7.3. Multiple Comparisons and Multiplicity

The study co-primary hypotheses are the (statistical) one-sided superiority of a TVB-2640 50-mg dose over placebo based on each of the two co-primary efficacy endpoints at the 0.05 significance level, where a higher responder proportion is a better outcome. The statistical analysis (one-sided) test (CMH) of the primary hypothesis is declared if $p < 0.05$. No adjustment for the two co-primary efficacy tests will be performed, both will be tested at the 0.05 level using one-sided tests.

Both one-sided and two-sided 0.05 significance level tests will be used for the efficacy endpoints. The table below specifies whether the test of significance is one- or two-sided along with the expected direction of effect. No other control for multiplicity will be provided.

Note that endpoints that are being tested as one-sided will also have the two-sided p-values provided. Both 90% and 95% two-sided confidence intervals will be shown.

7.4. Efficacy Endpoints: 1-sided and 2-sided Testing Allocation

Endpoint Number	Endpoint Description	1-sided or 2-sided	Directionality for better outcome for 1-sided tests
	Co-Primary Efficacy Endpoints		
1A	Proportion of subjects experiencing histological improvement at Week 52 in NAS (i.e., ≥ 2 points improvement in NAS with ≥ 1 point improvement in ballooning or inflammation) and without worsening of fibrosis (by NASH CRN fibrosis score)	1-sided	Higher
1B	Proportion of subjects experiencing both of the following at Week 52: 
○ Resolution of steatohepatitis and no worsening of liver fibrosis (by NASH CRN fibrosis score). Resolution of steatohepatitis is defined as absence of fatty liver disease or isolated or simple steatosis without steatohepatitis and a NAS of 0 or 1 for inflammation, 0 for ballooning, and any value for steatosis.	1-sided	Higher

Endpoint Number	Endpoint Description	1-sided or 2-sided	Directionality for better outcome for 1-sided tests
	AND 
 ○ Histological improvement in NAS (≥ 2 points improvement in NAS). 		
	Secondary Efficacy and Pharmacodynamic Endpoints		
2	Proportion of MRI-PDFF $\geq 30\%$ responders at Week 26, where an MRI-PDFF $\geq 30\%$ responder is defined as a subject with $\geq 8\%$ liver fat content at Baseline who achieves a relative reduction from Baseline in MRI-PDFF $\geq 30\%$.	2-sided	
3	Proportion of MRI-PDFF $\geq 30\%$ responders at Week 52, where an MRI-PDFF $\geq 30\%$ responder is defined as a subject with $\geq 8\%$ liver fat content at Baseline who achieves a relative reduction from Baseline in MRI-PDFF $\geq 30\%$.	2-sided	
4	Proportion of MRI-PDFF $\geq 50\%$ responders at Week 52, where an MRI-PDFF $\geq 50\%$ responder is defined as a subject with $\geq 8\%$ liver fat content at Baseline who achieves a relative reduction from Baseline in MRI-PDFF $\geq 50\%$.	2-sided	
5	Proportion of subjects with improvement in liver fibrosis ≥ 1 stage by NASH CRN fibrosis score without worsening of steatohepatitis (defined as no increase in NAS for ballooning, inflammation, or steatosis) at Week 52.	1-sided	Higher
6	Proportion of subjects with improvement in liver fibrosis ≥ 1 stage by NASH CRN score without increase of total NAS score at Week 52.	1-sided	Higher
7	Proportion of subjects with improvement in liver fibrosis ≥ 1 stage by NASH CRN score without any worsening of NASH (defined as no worsening of ballooning and lobular	1-sided	Higher

Endpoint Number	Endpoint Description	1-sided or 2-sided	Directionality for better outcome for 1-sided tests
	inflammation; a 1 grade change in steatosis may be acceptable) at Week 52.		
8	
Proportion of subjects experiencing both of the following at Week 52:
 
 ○ Resolution of steatohepatitis on overall histopathological reading and no worsening of liver fibrosis on NASH CRN fibrosis score. Resolution of steatohepatitis is defined as absent fatty liver disease or isolated or simple steatosis without steatohepatitis and a NAS score of 0-1 for inflammation, 0 for ballooning, and any value for steatosis 
AND
 
 ○ Improvement in liver fibrosis greater than or equal to one stage (NASH CRN fibrosis score) and no worsening of steatohepatitis (defined as no increase in NAS for ballooning, inflammation, or steatosis). 	1-sided	Higher
9	
Proportion of subjects experiencing both of the following at Week 52:
 
 ○ Histological improvement at Week 52 in nonalcoholic fatty liver disease (NAFLD) activity score (NAS) (i.e., ≥ 2 points improvement in NAS with ≥ 1 point improvement in ballooning or inflammation) and without worsening of fibrosis (by NASH Clinical Research Network [CRN] fibrosis score) 
AND
 
 ○ Improvement in liver fibrosis greater than or equal to one stage 	1-sided	Higher

Endpoint Number	Endpoint Description	1-sided or 2-sided	Directionality for better outcome for 1-sided tests
	(NASH CRN fibrosis score) and no worsening of steatohepatitis (defined as no increase in NAS for ballooning, inflammation, or steatosis).		
10	Proportion of subjects experiencing resolution of steatohepatitis and no worsening of liver fibrosis (by NASH CRN fibrosis score). Resolution of steatohepatitis is defined as absence of fatty liver disease or isolated or simple steatosis without steatohepatitis and a NAS of 0 or 1 for inflammation, 0 for ballooning, and any value for steatosis at Week 52.	1-sided	Higher
11	Proportion of subjects with histological improvement (decrease) at Week 52 in NAS by ≥ 1 point.	1-sided	Higher
12	Proportion of subjects with histological improvement (decrease) at Week 52 in NAS by ≥ 2 points.	1-sided	Higher
13	Change and percent change from Baseline in MRI-PDFF liver fat (%) at Week 26.	2-sided	
14	Change and percent change from Baseline in MRI-PDFF liver fat (%) at Week 52.	2-sided	
15	Proportion of subjects with NASH resolution (defined as absence of fatty liver disease or isolated or simple steatosis without steatohepatitis and a NAS of 0 or 1 for inflammation, 0 for ballooning, and any value for steatosis) at 52 weeks.	1-sided	Higher
16	Change from Baseline in ALT, AST, ALP, and GGT at Weeks 26 and 52 and at each study visit.	2-sided	
17	Change from Baseline in LDL-C and other lipid levels (including LDL/HDL ratio) at Weeks 26 and 52 and at each study visit.	2-sided	

Endpoint Number	Endpoint Description	1-sided or 2-sided	Directionality for better outcome for 1-sided tests
18	Change from Baseline in collagen/fibrous area and fibrosis score, assessed by digital pathology, at Week 52.	1-sided	Lower
19	Changes from Baseline in metabolic parameters, including fasting insulin, fasting glucose, HOMA-IR, adipon-IR, and HbA1c levels at Weeks 26 and 52 and at each study visit.	2-sided	
20	Change from Baseline in FGF-21, adiponectin, and other NASH biomarker levels at Weeks 26 and 52 and at each study visit.	2-sided	
21	Change from Baseline in FibroScan (Liver Stiffness Measure (kPa)) and CAP score results at Weeks 26 and 52.	1-sided	Lower
22	Change from Baseline in PRO-C3 and other fibrosis biomarkers at Weeks 4, 13, 26, and 52.	2-sided	
23	Change from Baseline in ELF score at Weeks 26 and 52.	2-sided	
24	Plasma concentrations of TVB-2640 at Weeks 1, 4, 13, 26, and 52.	N/A	
	Exploratory Efficacy and Pharmacodynamic Endpoints		
25	Proportion of MRI-PDFF $\geq 30\%$ responders at Week 52 who have ≥ 17 U/L reduction in ALT.	2-sided	
26	Change from Baseline in FAST score at Weeks 26 and 52.	1-sided	Lower
27	Change from Baseline in Agile 3+ score at Weeks 26 and 52.	1-sided	Lower
28	Change from Baseline in levels of select fibrosis biomarkers (e.g., TIMP-1) at Weeks 4, 13, 26, and 52.	2-sided	

Endpoint Number	Endpoint Description	1-sided or 2-sided	Directionality for better outcome for 1-sided tests
29	Change from Baseline in levels of lipidomic/metabolomic biomarkers (e.g., tripalmitin, ceramides, bile acids, diacylglycerols, and other classes of metabolites) at Weeks 4, 13, 26, and 52.	2-sided	
30	Change from Baseline in HbA1c levels among subjects with T2DM at Weeks 13, 26, 39, and 52.	2-sided	
31	Change from Baseline in FIB-4 at Weeks 4, 13, 26, and 52.	2-sided	
32	Change from Baseline in additional fibrosis parameters such as zonal analyses of fibrosis, NAS, and individual NAS components as determined by digital pathology at Week 52.	N/A*	
33	Correlation of changes in MRI-PDFF with changes in other endpoints.	N/A*	
34	Presence or absence of SNPs relevant for NASH.	N/A	
35	Correlation of predictive signature with other endpoints.	N/A*	
36	Correlation of lipids (e.g. tripalmitin) with other endpoints.	N/A*	
37	Change from Baseline in gut microbiome analyses at Weeks 26 and 52 in a substudy of subjects.	N/A*	
38	Change from Baseline in HepVita Nutritional Survey at Weeks 26 and 52 in a substudy of subjects.	N/A*	
39	Change in MELD score from baseline to Week 52	1-sided	Lower

* These endpoints may be analyzed at a later date.

7.5. Reference Dates

- Screening date is defined as the electronic case report form (eCRF) provided date on which a subject was screened for study entry.
- Randomization date is defined as the date on which the subject is randomized to study treatment.
- Treatment start date is defined as the date of first dose of study drug (also referred to as Day 1).
- Treatment end date is defined as the date of last dose of study drug.
- The calculation of age will use the informed consent date as its reference date.
- Safety data, such as AEs and laboratory assessments will use the treatment start date as a reference date to assign treatment emergence.
- Study day will be based on treatment start date as a reference date.

Reference day calculations will be defined as:

- date of interest – reference date + 1 when the date of interest \geq reference date.
- otherwise, date of interest – reference date.

For example, duration of treatment is defined as treatment end date – treatment start date + 1.

If either date is missing, reference date calculations will not be performed.

7.6. Baseline and Post-Baseline Changes

Unless stated otherwise, baseline will be based on the last non-missing value collected prior to the start of study treatment based on the treatment start date and time, if applicable. Post-baseline values will be those collected after the treatment start date and time, if applicable.

Change from baseline is defined as: post-baseline value – baseline value.

Percentage change from baseline is defined as: $(\text{post-baseline value} - \text{baseline value})/\text{baseline value} \times 100\%$.

7.7. Handling Below Limit of Quantification (BLQ) or Lower Limit of Quantification (LLOQ) Values

Any parameters with values identified as $<x$, $\leq x$, $>x$, or $\geq x$ will be analyzed using the ‘x’ value (the analysis will ignore the $<$, \leq , $>$, or \geq symbol).

7.8. Imputation of Partial Dates

Imputed dates will be used to classify treatment emergent AEs (TEAEs) and prior and concomitant medications.

Adverse Events

- If the AE start date is completely missing the event will be assumed to have started on the first day of treatment and will be considered a TEAE. If a subject was not treated, then no imputation will be conducted for missing start dates.
- If the AE start date is missing day and month, do the following:
 - If the AE start year is the same year as that of the first treatment and the AE contains information to indicate that the event ended before the treatment start date (e.g., AE end date month and year are earlier than the treatment start date or the full AE end date is known and occurs earlier than the treatment start date), then set the AE day/month to '1 January'.
 - If the AE start year is the same as that of the first treatment and the AE contains information to indicate that the event ended after the treatment start date, then set the AE start day/month to the treatment start day/month
 - If the AE start year is later than that of the first treatment, then set the AE start day/month to '1 January.'
 - If the AE start year falls before that of the first treatment, then the AE start day/month will not be imputed.
- If only the AE start day is missing, do the following:
 - If the AE start year is the same year as that of the first treatment and the AE month is prior to the first treatment date, then set the AE day to '1'.
 - If the AE start month/year are the same as that of the first treatment and the AE contains information to indicate that the event ended before the treatment start date (e.g., the full AE end date is known and occurs earlier than the treatment start date), then set the AE day to '1'.
 - If the AE start month/year are the same as the first treatment and the AE end date is after the treatment start date, then set the AE day to the same day as treatment start day.
 - If the AE start year is the same as that of the first treatment and the AE start month is after the first treatment, or the AE start year is later than that of the first treatment, then set AE day to '1'.
- AE end dates will not be imputed.

Prior and Concomitant Medications

- The imputation rules for AE start dates will be used for prior and concomitant medication start dates.
- Prior and concomitant medication stop dates will be imputed as follows:
 - If the stop date is only missing the day, then the stop day is the last day of the month
 - If the stop date is missing both the day and month, then the stop month and day is December 31

- If the stop date is completely missing, no imputation is performed, and the medication will be classified as a concomitant medication for subjects who were treated.

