10.1. Adverse Events

An AE is any untoward medical occurrence in a subject or clinical investigation subject administered a pharmaceutical product, and which does not necessarily have to have a causal relationship with this treatment. An AE can therefore be any unfavorable and unintended sign (including abnormal laboratory findings), symptom, or disease temporally associated with the use of an investigational product, whether related to the investigational product or not.

An unexpected AE is any event for which the nature or severity is not consistent with the information in the current Investigator's Brochure.

Any abnormal clinical or laboratory finding considered by the Investigator to be clinically significant is to be recorded in the eCRF as part of the subject's medical history if occurring prior to the start of study drug administration and as an AE if occurring after the start of study drug administration at baseline, where the finding represents a change from baseline.

A treatment emergent AE (TEAE) is defined as any AE occurring after the first dose of study treatment. All summaries of AEs will be based on TEAEs. All AEs recorded on the eCRF, whether treatment emergent or not, will be presented in the data listing. Non-TEAEs will be flagged in the listings.

Adverse Events will be coded using MedDRA version 24.0 or higher for reporting by SOC and PT. Summaries of TEAEs by SOC and PT will be presented in descending order of overall incidence. TEAEs will also be summarized by maximum intensity as classified according to the National Cancer Institute (NCI) Common Terminology Criteria for Adverse Events (CTCAE), Version 5.0 (or higher). If the AE is not included in the NCI CTCAE, then the Investigator is to determine the severity of the AE according to the criteria provided in the study protocol.

The causal relationship of each AE to study drug will be determined by the Investigator according to best medical judgment as definitely related, probably related, possibly related, unlikely related, or unrelated. If the relationship between the AE and study drug is determined to

be “possible”, “probable”, or “definite”, the event will be considered treatment-related for the safety analyses.

Missing severity assessments will be listed as missing information. Missing relationship assessments will also be listed as missing information. All AE summaries will be produced using the safety population and displayed by treatment group and overall.

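### SAP 7.8 counts an adverse event with a completely missing start date as treatment-emergent even when it ended before first dose, and has no rule for some partly dated events around first dose

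*SAP*

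**What the plan says.** SAP 7.8 states the purpose of the rules: "Imputed dates will be used to classify treatment emergent AEs (TEAEs) and prior and concomitant medications". For AE start dates it distinguishes three cases.

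- **Start completely missing.** "If the AE start date is completely missing the event will be assumed to have started on the first day of treatment", and the event is a TEAE. The only exception is a subject who was never treated.
- **Day and month missing, year equal to the first-dose year.** If the record shows that the event ended before first dose, the start becomes 1 January. The other branch opens "If the AE start year is the same as that of the first treatment and the AE contains information to indicate that the event ended" and continues with the condition that it ended after treatment start; the start then takes the first-dose day and month.
- **Day missing, month and year equal to those of first dose.** If the event ended before first dose, the day becomes 1. The other branch reads "If the AE start month/year are the same as the first treatment and the AE end date is after the treatment start date"; the day then becomes the first-dose day.

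The section adds: "AE end dates will not be imputed". SAP 7.5 says of its date calculations: "If either date is missing, reference date calculations will not be performed". SAP 10.1 defines a TEAE as an AE occurring after the first dose and says: "All summaries of AEs will be based on TEAEs". Protocol 13.3 defines it as an AE that appears after treatment starts, or was present at the start and worsened.

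**The concern.** The completely-missing rule gives a wrong class whenever the end date is known and precedes first dose. Such an event can meet neither the SAP nor the protocol definition of a TEAE, and its imputed start falls after its end. These records are possible. The protocol collects AEs from consent (12.2.3), screening may begin up to 90 days before randomization (7.1), and complications of a protocol-mandated biopsy are AEs (12.2.1.1).

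The partial-date branches raise a different problem. Both of their outcomes depend on end-date information that places the end strictly before or strictly after first dose. A record without it gets no imputed start date, and the programmer has to choose. The SAP gives skin and eye TEAEs their own tables (10.1) and subgroups defined by COVID-19 diagnosis or vaccination within 30 days of onset (7.2), so both the TEAE flag and the onset date are used.

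**Working it through.** The plan gives no figure to reproduce. The check applies the SAP 7.8 rules literally to seven start-date patterns crossed with seven end-date patterns, using an assumed first dose of 15 June 2022. These are the combinations that matter:

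| Start recorded | End recorded | Imputed start | Status |
|---|---|---|---|
| none | 10 Jun 2022 | 15 Jun 2022 | TEAE, although over before first dose |
| none | May 2022 | 15 Jun 2022 | TEAE, although over before first dose |
| Jun 2022 | 10 Jun 2022 | 1 Jun 2022 | pre-dose |
| Jun 2022 | 20 Jun 2022 | 15 Jun 2022 | TEAE |
| Jun 2022 | ongoing | no rule | undefined |
| Jun 2022 | 15 Jun 2022 | no rule | undefined |
| Jun 2022 | Jun 2022 | no rule | undefined |
| 2022 | 10 Jun 2022 | 1 Jan 2022 | pre-dose |
| 2022 | May 2022 | 1 Jan 2022 | pre-dose |
| 2022 | 20 Jun 2022 | 15 Jun 2022 | TEAE |
| 2022 | ongoing, 15 Jun 2022, or Jun 2022 | no rule | undefined |

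**Completely missing start.** In the first row the imputed start is 15 − 10 = 5 days after the recorded end. An event with the same end date but a start recorded as June 2022, or only as 2022, is correctly placed before first dose. The section thus uses the end date when part of the start is known and ignores it when none is.

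**No-rule cases.** An ongoing event has no end date to test and none is imputed. An end on the first-dose date is neither before nor after it. An end recorded only as the first-dose month does not settle the order. The section has no default for these.

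**Effect of one record.** The planned arms are 108 and 54 subjects (SAP 4.3). Assuming all are dosed, moving one subject into or out of a preferred-term row changes it by 1/108 = 0.9 percentage points on TVB-2640, or 1/54 = 1.9 points on placebo. How many records are affected depends on the frequency of missing and partial dates, which the documents do not give.

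**The case against.** The best defence is that few records will be affected. The investigator must report an onset date for every AE (Protocol 12.2.3), and eCRFs are complete only when missing data are resolved (15.3). A known end date with not even a start year is unusual, above all for a biopsy complication, whose onset is bounded by a recorded procedure. SAP 10.1 also sends clinically significant abnormal findings from before dosing to medical history, which shrinks the pool of pre-dose AEs. It does not empty it, since the same section expects non-TEAEs and flags them in the listings. All AEs are listed and safety is descriptive (SAP 10), so nothing is hidden. This limits the size of the problem; it does not make the completely-missing rule correct.

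Three stronger readings are tempting, and the documents support none of them.

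- *Ongoing events with an unknown start day are misclassified as not treatment-emergent.* The SAP gives them no class. The SAP 7.5 sentence concerns day arithmetic, and a missing date does not always prevent classification: a medication with no stop date is still classed as concomitant for treated subjects (SAP 7.8). An analyst could sensibly read ongoing as ending after treatment start. The event may also have begun earlier in the month, before first dose.
- *Any event that ended before first dose is counted as a TEAE.* This holds only when the start date is completely missing. In the first-dose month and year, the partial-date branches place events shown to have ended before first dose correctly.
- *Skin and eye events are the ones lost, because they persist.* Protocol 5.2 reports that all TEAEs in the China cohort resolved, although dry eye (8 of 21 treated) and skin exfoliation (7 of 21) were common there.

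**Conclusion.** The point holds in two parts of unequal weight. The completely-missing rule, as stated, gives a wrong result for any event known to have ended before first dose; it conflicts with SAP 10.1 and with the end-date checks elsewhere in SAP 7.8. The gap in the partial-date branches is missing detail: TEAE status is undefined, with a risk that the event is left out of the tables or classed by programmer choice. Analysts would probably resolve it sensibly, so alone it would be minor. The likely effect on the safety tables is small. The conclusion rests on a literal reading of SAP 7.8 and on AEs from the screening period being in the AE data, as the protocol requires. It does not depend on the illustrative dates.

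**What to change.** Make two changes in SAP 7.8.

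(a) Add to the completely-missing rule: *unless the available end-date information, full or partial, shows that the event ended before the treatment start date, in which case it is not a TEAE*.

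(b) In both partial-date branches, replace the condition that the event ended after treatment start with a default: *otherwise, including ongoing events and missing or inconclusive end dates, set the missing start day, or day and month, to those of the treatment start date*.

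With (a), the first two rows of the table become non-TEAEs. With (b), every no-rule row gets a start of 15 June 2022 and counts as a TEAE. This is a convention that counts doubtful events as treatment-emergent, and some of them may in fact have begun before first dose. Medication start dates borrow the AE rules, so the new wording should be checked there too; the prior or concomitant class itself turns on the stop date (SAP 8.6).

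The cost is two clauses of SAP text and the matching derivation code. No new data are needed. The change belongs in the version approved before unblinding, as SAP 2 requires.
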